5.2 Methods for Handling Missing Data

No imputation of missing data will be performed on data that is not PK.

6 STUDY SUBJECTS

Unless otherwise specified, all available data will be listed and summary table for disposition will be presented for the safety population.

6.1 Disposition

Subject disposition will be summarized by treatment sequence and overall, including:

- Number of subjects screened
- Number of subjects randomized
- Number of subjects who received any treatment compound (morphine, AZD4041 or placebo)
- Number of subjects who received IP (i.e. AZD4041 or placebo)
- Number (%) of subjects who completed the study

- Number (%) of subjects discontinued from the study overall and by primary reason for discontinuation
- Number (%) of subjects included in each of the analysis populations

The percentages will be calculated using the number of subjects who received at least one dose of a treatment.

Listings of subject's disposition and subjects included in each of the analysis populations will be provided.

6.2 Protocol Deviations

Deviations will be collected in the clinic deviation tracking system (DTS) and presented in a general protocol deviation listing.

7 DEMOGRAPHIC AND OTHER BASELINE CHARACTERISTICS

Unless otherwise specified, all available data will be listed and summary tables for demographics and other baseline characteristics will be presented for the safety population.

Medical history will be recorded during screening.

Demographic and baseline characteristics including age, height, weight (at screening), and body mass index (BMI) will be listed and summarized by treatment sequence and overall. Descriptive statistics will be presented for age, height, weight, and BMI, while frequency counts and percentages will be presented for sex, ethnicity, and race.

The following will be presented in listings:

- Medical history
- Prior and concomitant medications
- Childbearing potential and contraceptive method
- Alcohol habits
- Smoking habits
- Recreational drug use history (Amphetamines, barbiturates, cannabinoids, cocaine, opiates, benzodiazepines, ethanol, and phencyclidine)

8 PHARMACOKINETIC ANALYSIS

The pharmacokinetic (PK) parameters from the concentration data for AZD4041, morphine, morphine-6-glucuronide and morphine-3-glucuronide will be derived using non-compartmental methods in Phoenix® WinNonlin® Version 8.3 or higher (Certara) by the Clinical PK Scientist from AstraZeneca.

8.1 Handling of Measurements Below the Lower Limit of Quantification in the PK analysis

For each PK sampling period, plasma concentrations that are non-quantifiable (NQ) from the time of pre-dose sampling ($t=0$) up to the time of the first quantifiable concentration is set to a value of zero. After this time point, NQ plasma concentrations are set to missing for all

concentration profiles. Where 2 or more consecutive concentrations are NQ at the end of a profile, the profile is deemed to have terminated and therefore any further quantifiable concentrations are set to missing for the calculation of the PK parameters unless it is considered to be a true characteristic of the profile of the drug.

If an entire concentration-time profile is NQ, the profile is excluded from the PK analysis.

Cmax, tmax, and tlast are taken directly from the concentration-time profiles.

8.2 Handling of Measurements Below the Lower Limit of Quantification in the TFLs

Individual concentrations below the LLOQ of the bioanalytical assay are reported as NQ in the listings with the LLOQ defined in the footnotes of the relevant TFLs. Individual plasma concentrations that are Not Reportable are reported as NR and those that are missing are reported as NS (No Sample) in the listings. Plasma concentrations that are NQ, NR or NS are handled as follows for the provision of descriptive statistics:

- Any values reported as NR or NS are excluded from the summary tables and corresponding figures.
- At a time point where less than or equal to 50% of the concentration values are NQ, all NQ values are set to the LLOQ, and all descriptive statistics are calculated accordingly.
- At a time point where more than 50% (but not all) of the values are NQ, the gmean and gCV% are set to Not calculable (NC). The maximum value is reported from the individual data, and the minimum and median are set to NQ.
- If all concentrations are NQ at a time point, no descriptive statistics are calculated for that time point. The gmean, minimum, median and maximum are reported as NQ and the gCV% as NC.
- The number of values below LLOQ ($n < \text{LLOQ}$) are reported for each time point together with the total number of collected values (n).

Three observations $> \text{LLOQ}$ are required as a minimum for a plasma concentration or PK parameter (e.g. Cmax, Cmax,ss) to be summarised. Two observations $> \text{LLOQ}$ are presented as minimum and maximum with the other summary statistics as NC.

8.3 Actual Time

PK analysis is, where data allow, carried out using actual elapsed times determined from the PK sampling and dosing times recorded in the database. If actual elapsed times are missing, nominal times may be used at the discretion of the PK Scientist with approval from the AZ Clinical Pharmacology Scientist (CPS). Nominal sampling times may be used for any agreed interim PK parameter calculations.

8.4 Non-Compartmental Analysis

The PK parameters for AZD4041 are presented in [Table 8-1](#).

Table 8-1 Pharmacokinetic Parameters of AZD4041

Parameter	Definition	Calculation
The following plasma PK parameters will be calculated for Days 2 to 15		
C_{trough}	Predose concentration observed immediately prior to the next successive dose	
The following plasma PK parameters will be calculated for Days 8 and 15		
$C_{max,ss}$	Maximum observed plasma concentration at steady-state	
$t_{max,ss}$	Time to reach peak or maximum observed concentration following drug administration at steady-state	
$AUC\tau$	Area under the concentration time curve over the dosing interval at steady state, calculated from 0 to 24 hours (dosing interval)	Using the linear up/log down trapezoidal rule
$t_{1/2\lambda z}$	Half-life associated with terminal slope (λz) of a semi-logarithmic concentration-time curve (Day 15 only)	Using the linear up/log down trapezoidal rule $\ln(2)/\lambda z$
C_{av}	Average concentration during a dosing interval at steady-state	$AUC\tau/\tau$
CL_{ss}/F	Apparent total body clearance at steady state	Dose/ $AUC\tau$
Vz_{ss}/F	Apparent volume of distribution at steady state, based on the terminal phase	$(CL_{ss}/F)/\lambda z$
The following urine PK parameters will be calculated for AZD4041(Day 15 only)		
$A\tau$	Cumulative amount of unchanged drug excreted into urine over a dosing interval τ	Sum of amount excreted in the urine over the dosing interval τ
$A\tau_{1-t2}$	Amount of unchanged drug excreted into urine over a specified collection interval	Urine Volume for the specified collection interval (0-6, 6-12, 12-24, etc...)
$F\tau/F$	Apparent percentage of dose excreted unchanged in urine over a dosing interval	$(A\tau/Dose)*100$ or $(CL_R/CL)*100$

Parameter	Definition	Calculation
Fe0-x/F	Apparent percentage of dose excreted unchanged in urine over a specified period of time.	$(Ae0-x/Dose) * 100$ with $x = 6, 12, \text{ and } 24$.
CL _R	Renal clearance	$Ae\tau/AUC\tau$
t _{1/2}	Elimination half-life (on Day 15 only)	$\ln(2)/\lambda z$

The PK parameters for morphine, morphine-6-glucuronide and morphine-3-glucuronide on Days 1 and 15 are presented in [Table 8-12](#).

Table 8-2 Pharmacokinetic Parameters of Morphine, morphine-6-glucuronide and morphine-3-glucuronide in Plasma (Days 1 and 15)

Parameter	Definition	Calculation
C _{max}	Maximum observed concentration (Parent and Metabolites)	
t _{max}	Time of maximum observed concentration. If the maximum observed concentration is not unique, then the first maximum is used (Parent and Metabolites)	
AUC _{0-t}	Area under the plasma concentration-time curve from time of last dosing to the time of last quantifiable concentration (t _{last}) (Parent and Metabolites)	Using the linear up/log down trapezoidal rule
AUC _{0-∞}	Area under the plasma concentration-time curve extrapolated to infinity (Parent and Metabolites)	$AUC_{0-t} + C_{last}/\lambda z$ where C_{last} is the last quantifiable concentration at t_{last}
t _{1/2} λz	Terminal elimination half-life (Parent and Metabolites)	Using the linear up/log down trapezoidal rule $\ln(2)/\lambda z$
t _{last}	Time of last measurable observed concentration (Parent and Metabolites)	
CL	Total body clearance (Parent drug only)	Dose/ AUC _{0-∞}
V _z	Volume of distribution based on the terminal phase (Parent drug only)	CL/λz

Additional PK parameters may be calculated if deemed appropriate

The diagnostic PK parameters for AZD4041, morphine, morphine-6-glucuronide and morphine-3-glucuronide on Days 1, 8, and 15, as appropriate, are presented in [Table 8-13](#). These parameters will not be summarized but will be listed.

Table 8-3 Diagnostic PK Parameters for all Analytes in Plasma

Parameter	Definition	Calculation
λ_z	Terminal elimination rate constant	Estimated from linear regression of the terminal part of the log concentration versus time curve
λ_z lower	Lower (earlier) t used for λ_z determination	
λ_z upper	Upper (later) t used for λ_z determination	
$\lambda_z N$	Number of data points used for λ_z determination	
λ_z span ratio	Time period over which λ_z was determined as ratio of $t_{1/2}/\lambda_z$	$(\lambda_z \text{ Upper} - \lambda_z \text{ lower})/(t_{1/2}/\lambda_z)$
Rsq adj	Statistical measure of fit for the regression used for λ_z determination adjusted for the number of used data points (n obs)	
AUCextr	Extrapolated area under the curve from t_{last} to infinity, expressed as percentage of AUC _{inf}	

8.4.1 Urine PK Parameters

Urine PK analysis is performed where there are quantifiable urine concentrations and available volume data from post-dose collection periods, using nominal time intervals. Urine concentrations below lower limit of quantification (LLOQ) are treated as numerical zero.

In cases of incomplete urine collection in any of the specified collection intervals (e.g. spilled sample), the calculation and reporting of urine PK parameters are at the discretion of the PK Scientist with approval from the AZ Clinical Pharmacology Scientist (CPS).

8.4.2 Plasma PK Parameters

For each analyte, plasma concentrations for each scheduled time-point are summarised by PK Day and Treatment sequence using appropriate descriptive statistics. Similar data (e.g. single dose or multiple dose for the same dosing regimen) from different Study Parts or PK Days/Visits may also be summarised together.

The following descriptive statistics are presented for plasma concentrations:

- n
- n below LLOQ
- geometric mean (gmean)
- geometric coefficient of variation (%) (gCV)
- arithmetic mean (mean)
- arithmetic standard deviation (Std Dev)
- median
- minimum (min)
- maximum (max)

The gmean is calculated as $\exp(\mu)$, where μ is the mean of the data on the natural log scale.

The gCV is calculated as $100 \times \sqrt{\exp(s^2) - 1}$, where s is the Std Dev of the data on the natural log scale.

Where required for plots: The gSD is calculated as $\exp(\sigma)$, where σ is the standard deviation of the data on the natural log scale. The gmean \pm gSD (gmean-gSD and gmean+gSD) are calculated as $\exp[\mu \pm s]$.

Protocol scheduled times are used to present the PK concentration summary tables and corresponding gmean concentration-time figures.

8.4.3 Urine Concentration Data

Urine concentration and volume/weight data are listed only and not summarised. Any individual data excluded from the PK analysis are flagged with an appropriate footnote in the listing by the PK Scientist.

8.5 Pharmacokinetic Statistical Methodology

8.5.1 PK Parameter Listings

All reportable PK parameters, including individual diagnostic and lambda z related parameters, are listed for each subject by PK Day and Treatment sequence, for each analyte separately.

8.5.2 PK Parameter Descriptive Statistics

All PK parameters are summarised for each analyte by PK Day and Treatment sequence using appropriate descriptive statistics. Similar parameter data (e.g. single dose or multiple dose for the same dosing regimen) from different PK Days may also be summarised together.

The descriptive statistics for PK parameters are presented as follows:

- Ctrough, Cmax, Cmax,ss, Cav, AUC τ , AUC0-t, AUC0- ∞ , $t^{1/2}\lambda z$, CL, CLss/F, Vz, Vzss/F, CLR, Ae and fe: present n, geometric mean, geometric standard deviation (Geo Std Dev), arithmetic mean of non log-transformed data (mean), arithmetic standard deviation (Std Dev), gCV(%), median, min and max.
- tmax, and tlast: present n, median, min and max.
- Diagnostic parameters (e.g. λz , λz lower, λz upper, λzN , λz span ratio, n obs, Rsq adj and AUCextr): present n, arithmetic mean, Std Dev, gmean, gCV%, median, min and max.

Three values are required as a minimum for PK parameters to be summarised. Two values are presented as a min and max with the other summary statistics as NC.

If one or more values for a given parameter is zero, then no geometric statistics are calculated for that parameter and the results for geometric statistics are set to NA (Not Applicable).

The point estimate and associated two-sided 90% confidence intervals for the ratio of PK parameters (for AZD4041: AUC τ , Cmax,ss, Ctrough,ss; for morphine and metabolites: Cmax, AUC0-t, AUC0- ∞) for each comparison of interest will be calculated:

For treatment sequence 1:

- AZD4041 in the absence of Morphine - Day 8 and AZD4041 in the presence of Morphine – Day 15
- Morphine in the absence of AZD4041 – Day 1 and Morphine in the presence of AZD4041 – Day 15
- Morphine metabolites in the absence of AZD4041 – Day 1 and Morphine metabolites in the presence of AZD4041 – Day 15

For treatment sequence 2:

- Morphine on Day 1 and 15.
- Morphine metabolites on Day 1 and 15.

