## 5.3. Administration of Study Drug

Study treatments as described in Section 3.2 will be administered in the morning. The date and time of each dose will be recorded. For each subject, Day 1 to Day 14 scheduled postdose activities and assessments will be performed relative to the time of AZD4041/placebo administration or end of morphine infusion. From Day 15, all scheduled postdose activities will be performed relative to the end of morphine infusion, with the exception of PK sampling for AZD4041.

On Day 1, a single intravenous infusion of morphine will be administered to the subjects over a 10-minute interval ( $\pm$  30 seconds) in the morning.

On Days 2 to 15, an oral dose of the assigned treatment (either AZD4041 or Placebo) once daily will be administered to subjects using a syringe for 14 consecutive days. The dose will be administered directly into the subject's mouth.

On the morning of Day 15, the oral dose of the assigned treatment (either AZD4041 or Placebo) will be combined with a single intravenous infusion of morphine. A single intravenous infusion of morphine will be administered to the subjects over a 10-minute interval ( $\pm$  30 seconds). The assigned treatment (AZD4041 or Placebo) will then be administered orally immediately (within 1 minute) after the end of morphine infusion.

The study drugs will be dispensed only to eligible subjects and administered under the supervision of study personnel. Treatment compliance will be verified according to the site's standard operating procedures (SOPs).

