# Table 6-15Pharmacokinetic Blood Sampling Schedule for AZD4041Pharmacokinetic Blood Sampling - Scheduled Timepointsa

Days 2 to 7: predose

Day 8: predose, 5, 15, 30 minutes and 1, 1.5, 2, 3, 4, 6, 8, and 12 hours postdose

Days 9 to 14: predose

Day 15: predose, 5, 15, 30 minutes and 1, 1.5, 2, 3, 4, 6, 8, 12, 24, 36, 48, and 72 hours postdose

a. Nominal times listed are relative to the time of AZD4041 administration.

Blood samples will be collected by direct venipuncture into a labeled tube containing the appropriate anticoagulant as specified by the bioanalytical facility. As an option to the subject or if judged necessary by the clinical staff, blood samples may be collected from an indwelling cannula which will be placed in the vein of the subject.

The actual time of all PK blood draws will be recorded and reported for all subjects.

Windows for timed PK blood sample collections are presented in Table 6-16. PK samples collected outside of the pre-specified windows will be documented as protocol deviations. Since actual times are to be used for the PK analysis, deviations will be reflected in the analysis unless indicated otherwise upon review of the data.

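### SAP 8.5.2 and 8.5.3 add Ctrough,ss to the Day 15/Day 8 AZD4041 interaction ratio, but as defined it is a predose value that stays within about 2% of 1 and carries almost no information on morphine's effect

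*SAP*

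**What the plan says.** One secondary objective is to assess the impact of morphine on the steady-state PK of AZD4041 (protocol Section 2; SAP Table 2-1).

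- **SAP 8.5.2** plans "The point estimate and associated two-sided 90% confidence intervals for the ratio of PK parameters". For AZD4041 these are AUCtau, Cmax,ss and Ctrough,ss, and the Sequence 1 comparison is "AZD4041 in the absence of Morphine - Day 8 and AZD4041 in the presence of Morphine – Day 15". SAP 8.5.3 plots the same ratios.
- **SAP Table 8-1** defines Ctrough as "Predose concentration observed immediately prior to the next successive dose" and heads that row "The following plasma PK parameters will be calculated for Days 2 to 15". Ctrough,ss has no definition of its own.
- **Protocol 8.4.3.2** makes the same Day 15 versus Day 8 comparison on Cmax,ss and AUCtau only. Protocol 8.4.3.1 uses Ctrough only for a descriptive look at steady state.
- **Protocol 5.3** gives morphine on Day 15 over 10 minutes (± 30 seconds). AZD4041 "will then be administered orally immediately (within 1 minute) after the end of morphine infusion".
- **Protocol Table 6-15** times AZD4041 samples from the AZD4041 dose and schedules "Day 15: predose, 5, 15, 30 minutes and 1, 1.5, 2, 3, 4, 6, 8, 12, 24, 36, 48, and 72 hours postdose". Table 6-16 allows 5 minutes for a predose sample, relaxed only on Days 1 and 2.

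**The concern.** A trough that is meant to show what morphine did to AZD4041 must close a dosing interval that contained morphine. By the Table 8-1 definition the Day 15 trough closes the Day 14 interval, which contained none, and the Day 8 trough closes the Day 7 interval, which also contained none. The only earlier morphine dose, on Day 1, precedes both. The comparison is labelled as presence against absence of morphine, but for this parameter both sides are essentially without it.

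At stake is how one line of a table and one figure are read. A ratio close to 1 would appear beside AUCtau and Cmax,ss as a third estimate of the interaction. Protocol 1.3.2.1 already expects no appreciable effect of single morphine doses on AZD4041 clearance, so a value near 1 would look like agreement and the error would be easy to miss.

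**Working it through.** The documents give no expected ratio, power or margin for this comparison, so there is no planned figure to reproduce. The check asks how far each candidate ratio can move.

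**Inputs from the documents.** Effective half-life 18.6 to 21.3 h and AUC accumulation ratio 1.66 to 1.81 (protocol 1.3.2, multiple ascending dose study); once-daily dosing from Day 2; Day 15 timing as above.

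**Assumptions.** One compartment; tmax 1.5 h (documents: 0.5 to 3.0 h); morphine multiplies AZD4041 elimination by 0, 0.5 or 2 from the start of the Day 15 infusion, for 6 h or about 24 h. Effects on absorption are not modelled.

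**1. Check of the half-life.** With r = 2^(−24/t½), accumulation = 1/(1 − r).
- t½ 18.6 h: r = 0.409, accumulation 1.69.
- t½ 21.3 h: r = 0.458, accumulation 1.84.

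These lie within 2% of the documented 1.66 and 1.81.

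**2. Predose ratio with no morphine effect.** Six doses precede the Day 8 sample and 13 precede the Day 15 sample, so the ratio is (1 − r^13)/(1 − r^6).
- 18.6 h: 0.99999/0.99533 = 1.005.
- 21.3 h: 0.99996/0.99078 = 1.009.

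**3. When the Day 15 predose sample is drawn.** The latest point is the AZD4041 dose itself, at most 10.5 + 1 = 11.5 minutes after the infusion starts. A sample within 5 minutes of the dose falls during the infusion or up to a minute after it; one drawn earlier precedes the infusion.

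**4. Largest effect on the predose ratio.** If elimination stops entirely for 11.5 minutes, the trough is multiplied by exp(k × 11.5/60), with k = ln 2/t½: 1.0072 at 18.6 h and 1.0063 at 21.3 h.
- Elimination stopped: 1.0047 × 1.0072 = 1.012, and 1.0093 × 1.0063 = 1.016.
- Elimination doubled: 1.0047/1.0072 = 0.998, and 1.0093/1.0063 = 1.003.

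**5. The same scenarios across the parameters** (simulated; ranges are over the two half-lives).

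| Elimination | Predose ratio | C24 ratio, 6 h effect | C24 ratio, 24 h effect | AUCtau ratio, 24 h effect |
|---|---|---|---|---|
| Unchanged | 1.005–1.009 | 1.00 | 1.00 | 1.00 |
| Halved | 1.008–1.012 | 1.10–1.11 | 1.48–1.56 | 1.20–1.22 |
| Stopped | 1.012–1.016 | 1.21–1.24 | 2.19–2.44 | 1.45–1.52 |
| Doubled | 0.998–1.003 | 0.81–0.83 | 0.41–0.46 | 0.71–0.73 |

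C24 is the 24 h sample after the Day 15 dose divided by the Day 9 predose sample. Cmax,ss moves less than AUCtau here, from 0.96–0.97 (doubled) to 1.06 (stopped).

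**6. Smaller effects on C24.** If elimination falls to a fraction f for T hours, the ratio is about exp((1 − f) × k × T).
- T = 24 h: a 20% fall gives 1.17 to 1.20 and a 30% fall 1.26 to 1.31.
- T = 6 h: a 20% fall gives 1.04 to 1.05 and a 30% fall 1.06 to 1.07.

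**The case against.** **The definition can be read another way.** Taken as the end of each day's interval, the trough for Day 8 would be the Day 9 predose sample and the trough for Day 15 would be the 24 h sample. That is an informative ratio. The predose reading also has an awkward end: it yields a Day 2 trough before any AZD4041 has been given. This shows that the definition needs settling, but the predose reading is the better supported. The word used is predose, no dose follows Day 15, and the days listed are the days on which Table 6-15 schedules a predose sample. A programmer following Table 8-1 would take that sample.

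**The objective does not depend on Ctrough.** This stands. AUCtau and Cmax,ss, the only parameters in protocol 8.4.3.2, are kept in the SAP, and AUCtau responds clearly in the scenarios above.

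**Nothing is tested.** This also stands. A reader might infer that the plan tests for an interaction and would declare none from a trough ratio near 1. SAP 8.5.2 plans point estimates and 90% intervals, with no hypothesis, margin or no-effect criterion, and no document attaches a decision to this ratio.

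**The predose ratio has a use.** The Day 15/Day 8 comparison assumes that AZD4041 is at steady state by Day 8. Protocol 1.3.2 reports steady-state troughs at Day 6 or Day 8 depending on dose level, and here study Day 8 is only the seventh dosing day. A predose ratio helps to check that premise. This supports keeping it under a steady-state label, not under an interaction label.

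**Conclusion.** Under SAP Table 8-1 the Ctrough,ss ratio does not estimate morphine's effect on AZD4041. It stays within about 2% of 1 (0.998 to 1.016) from complete arrest to doubling of elimination. This rests on one-compartment kinetics, the documented half-lives and an effect that starts with the Day 15 infusion. The SAP gives no reason for going beyond the protocol's parameter list.

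The severity is minor to moderate: one of three reported parameters is uninformative and the secondary objective is still addressed. Two stronger readings are not supported. The sample is not guaranteed to precede all morphine exposure, because an in-window sample can fall during the infusion; the ratio is therefore not exactly 1, although the resulting shift is at most about 0.7% in these scenarios. Nor should the 17 to 31% movement in C24 be taken as the size of a missed interaction. It assumes a 20 to 30% fall in elimination lasting the full 24 h, a size and duration that no document states; a 6 h effect gives only about 4 to 7%.

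**What to change.** In SAP 8.5.2 and 8.5.3, do one of the following:

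1. Drop Ctrough,ss from the AZD4041 interaction ratio and its figure, which restores agreement with protocol 8.4.3.2.
2. Replace it with a defined end-of-interval concentration, C24: the 24 h sample after the Day 15 dose over the Day 9 predose sample.

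In either case, state in SAP Table 8-1 that Ctrough is the predose sample, use it only for the steady-state assessment, and limit it to Days 3 to 15, because the Day 2 predose sample precedes any AZD4041. A Day 15/Day 8 predose ratio may be kept if it is labelled as a steady-state check.

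The cost is SAP wording and programming. Both C24 samples are already in protocol Table 6-15: "Days 9 to 14: predose" covers Day 9, and the Day 15 schedule includes 24 h.
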